2c. Corticospinal excitability assessment: After the counting task assessment, participants will go through a series of corticospinal excitability assessement using single pulse transcranial magnetic stimulation (TMS, MagstimR Company, UK) . Surface electromyography (EMG) electrodes will be placed on the right Tibilias Anterior muscle with the participants seated on a reclining chair and wearing a pair of earplugs. EMG data will be sampled at 2000Hz and band-pass-filtered at 15-500Hz (Mega 600, Mega Electronics Ltd, Finland). The EMG data will be recorded and stored using MegaWin software (Mega Electronics Ltd, Finland) and analyzed offline using Matlab program (The Mathowroks, Inc, Natick MA). A Magstim 200 stimulator (Magstim Company, UK) will be used to deliver the TMS pulse via a double cone coil (Figure 1).

Figure 1. Double cone coil.

Neuronavigation system Brainsight TM (Rogue Research, Canada) will be used to reliably place the TMS coil over the scalp to precisely target the selected area. Stimulation will begin at 40% of maximum stimulator output and will be systematically increased to yield a motor evoked potential (MEP) from the tibialis anterior. A 'hot spot'of the right tibialis anterior will first to be determined. Hot spot is defined as the site at which the largest MEP is obtained at the lowest TMS stimulation intensity. Once the hot spot is determined, the resting motor thershold (RMT) will be defined. Resting motor threshold is the stimulation intensity that yield a MEP peak-to-peak amplitude > 50  $\mu$ V in 5 out of 10 consecutive trials. Once RMT is decided, the stimulation intensity

will be set at 120% RMT and 10 stimulations will be delivered to the hot-spot such that suprathreshold MEP can be recorded. These MEPs measures will be stored and analyzed offline to quantify corticospinal excitability.

3. **rTMS protocols:** After the corticospinal excitability assessment, participants will receive a high frequency rTMS applied to different areas at different visits.

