During each visit, they will receive 5Hz rTMS delivered to the target area (hot spot of the right tibialis anterior at the M1, left SMA, or left DLPFC). The 5Hz rTMS will be delivered in the form of 24 10-second trains with a 30second intertrain interval (a total of 1200 pulses) via a airfilled figure of 8 coil (Figure 2). The stimulation intensity will be set at 90% of individual RMT. We have previously shown that this protocol was effective to upregulate corticospinal excitability.

Figure 2. Air-filled coil for rTMS

After the rTMS protocol, corticospinal excitability will be reassessed using single pulse TMS again (procedure 2c). Participants will then perform the gait assessment (procedure 2a) and the counting task (procedure 2b).

Each participant will be tested for 3 visits (each visit will be 7±2days apart between two successive visits). Each visit will start with the assessment and be followed by a rTMS protocol. The target area for the rTMS protocols varies across visits (e.g. visit 1: Left SMA, visit 2: Left M1, and visit 3: Left DLPFC). The order will be pseudo-randomized and counterbalanced within each group.

4. Outcomes and data analysis: The primary outcome of this project is participant performance on the TUG test under single and dual-task conditions. The time taken to complete the TUG test under the two conditions will be used to derive dual-task cost (TUGdual – TUGsingle/TUGsingle). The dual-task cost will be compared across three rTMS protocols using repeated measure ANOVA. The secondary outcomes of the projects include gait parameters obtained from the

The secondary outcomes of the projects include gait parameters obtained from the GaitRite, MEPs measured under procedure 2c. These measures will be analyzed using repeated measure ANOVA as well.

b.	Is video recording a part of the s	tudy?	🛛 Yes 🗌 No	
	With sound $\square$	Without sound		
C.	Is audio recording a part of the s	tudv?		Yes 🗆 No

*If you answered "yes" to question #4b or 4c, describe the purpose of the recording and who will have access to these recordings.* 

The video recording will be used to quantify the number of corrected responses participants made on the counting task.

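### Repeating procedure 2c in full after rTMS resets the test pulse to 120% of a new threshold, which hides threshold-lowering gains from the MEP secondary outcome

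*Combined protocol and SAP*

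**What the plan says.** All of this is in section 4, Research Procedures.

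- **2c, Corticospinal excitability assessment**, is an ordered chain. The hot spot of the right tibialis anterior is located first. Then "Once the hot spot is determined, the resting motor thershold (RMT) will be defined", as the intensity that gives an MEP above 50 µV in 5 of 10 consecutive trials. The test intensity "will be set at 120% RMT and 10 stimulations will be delivered to the hot-spot such that suprathreshold MEP can be recorded". These MEPs are the stated measure of corticospinal excitability. The test intensity is given only as a multiple of RMT, never as a stimulator output to be held.
- **Item 3, rTMS protocols**, gives the post-stimulation step by cross-reference: after rTMS, "corticospinal excitability will be reassessed using single pulse TMS again (procedure 2c"). It also gives the expected direction: "We have previously shown that this protocol was effective to upregulate corticospinal excitability".
- **Item 4, Outcomes and data analysis**, names as secondary outcomes the gait parameters from "GaitRite, MEPs measured under procedure 2c", analysed by repeated measures ANOVA. RMT is not named, and no adjustment for RMT or for absolute test intensity is described.

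**The concern.** A test pulse tied to the threshold cannot show a change in that threshold. If 5 Hz rTMS lowers RMT at a site, the same stimulator output should evoke a larger MEP. Measuring RMT again and setting the pulse to 120% of the lower value takes that advantage away before the MEP is recorded.

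The MEP is the only named outcome that tests whether stimulation of M1, SMA or DLPFC changed corticospinal excitability. A flat MEP result at a site where the threshold did fall could be read as failed stimulation, and a null gait result would then be misinterpreted.

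There is also a precision cost. Any error in the repeated RMT moves the post-rTMS pulse, and so adds noise to the pre-to-post MEP change in a study of 10 participants.

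**Working it through.** **Step 1: reading the text.** Procedure 2c contains four steps: hot spot, RMT, pulse at 120% RMT, 10 MEPs. Item 3 invokes 2c after rTMS without excepting any of them, and nothing in the plan carries the pre-rTMS RMT or output forward. The literal result is a new RMT and a pulse at 120% of it.

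**Step 2: model.** The plan states no expected MEP or RMT change, so there is no figure of its own to reproduce. The size is illustrated with an assumed sigmoid recruitment curve:

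MEP(I) = P / (1 + exp((S50 − I)/k)), with RMT the intensity at which MEP = 0.05 mV.

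- From the plan: the 50 µV threshold criterion and the factor 1.2.
- Assumed: P = 1 mV; RMT = 50, 60 or 70% of stimulator output; k = 4, 6 or 8.
- For P = 1 mV, S50 = RMT + k·ln(1/0.05 − 1) = RMT + k·ln 19.

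**Step 3: one worked case (RMT 60, k 6, leftward shift of 3 points).**

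- S50 = 60 + 6 × 2.944 = 77.67. The pre-rTMS pulse is 1.2 × 60 = 72. Pre-rTMS MEP = 1/(1 + exp(5.667/6)) = 0.280 mV.
- After the shift, S50 = 74.67 and RMT = 57.
- Unchanged output, 72: MEP = 1/(1 + exp(2.667/6)) = 0.391 mV, or +39.5%.
- Reset output, 1.2 × 57 = 68.4: MEP = 1/(1 + exp(6.267/6)) = 0.260 mV, or −7.0%.

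**Step 4: why this happens.** Under a shift of d, the reset exponent is (S50 − d − 1.2(RMT − d))/k = (S50 − 1.2·RMT + 0.2d)/k. It is slightly larger than before rTMS, so the MEP falls slightly. If S50, k and RMT are all multiplied by f, the factor cancels and the MEP is unchanged for any parameter values.

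**Step 5: ranges over the nine curves (change from the pre-rTMS MEP).**

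| Assumed effect of rTMS | Unchanged output | 120% of new RMT |
|---|---|---|
| Leftward shift, 1 point | +9 to +16% | −2 to −3% |
| Leftward shift, 3 points | +24 to +47% | −6 to −9% |
| Leftward shift, 5 points | +35 to +79% | −9 to −15% |
| Proportional rescaling by 2 to 8% | +14 to +87% | 0% |
| Plateau 50% higher | +50% | −4 to +21% |
| Slope parameter k 10 to 20% smaller (steeper curve), RMT unchanged | +12 to +40% | +12 to +40% |

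The raised plateau also loses signal because the measured RMT falls with it. The last row loses nothing.

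**Step 6: noise with no true change.** Set the pulse at 1.2 × (RMT + e) on an unchanged curve. An error of e = ±1 point moves the MEP by −18 to +19%, and ±2 points by −33 to +38%. These figures are for one participant. If errors of 1 point, about 15% at RMT 60 and k 6, are independent, the effect on a mean over 10 is about 15%/√10 ≈ 5%.

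**The case against.** The strongest reply is that the text is ambiguous rather than wrong. A parenthetical cross-reference may mean only that the 10 pulses are repeated at the original setting, in which case nothing is masked. The reference cannot import every word of 2c anyway: 2c is placed after the counting task, whereas after rTMS it comes before gait and counting. This stands to the extent that the plan does not say outright that RMT is repeated. But the difference in order concerns timing and leaves the RMT step untouched, and no sentence supports holding the output. Two testers could follow different rules.

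Second, masking requires the gain to act through the threshold, and the plan does not say that it does. This stands: a steeper slope with RMT unchanged loses nothing, and the documents give no means of choosing among the mechanisms.

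Third, a full repeat of 2c would itself produce a post-rTMS RMT, so the threshold change would be observed. True, but RMT is not named as an outcome, so the plan makes no commitment to analyse or report it.

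Fourth, the curves and threshold errors are assumed, the noise averages down over participants, and only one secondary measure in a pilot is involved. All correct. These points limit the size and reach of the problem but do not justify leaving the test intensity tied to a quantity that rTMS may change.

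**Conclusion.** The concern holds. Following the cross-reference exactly gives a post-rTMS test pulse rescaled to the post-rTMS threshold, which is a poorer measure of the upregulation the plan expects. A threshold-lowering gain of tens of percent at unchanged output becomes zero or a small decrease. The zero under proportional scaling is algebraic; the other magnitudes depend on the assumed curves and are illustrative only.

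The conclusion has two conditions: 2c is repeated in full, and the gain acts at least partly by lowering the measured threshold. Confidence is medium because the first rests on reading a cross-reference. The plan should be corrected on this point, but the consequence is confined to the MEP secondary outcome.

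**What to change.** In item 3, state that the post-rTMS MEPs are recorded at the same hot spot and the same absolute single-pulse stimulator output as the pre-rTMS MEPs of that visit. In item 4, state that the within-visit pre-to-post MEP change is compared across the three sites and that RMT, if measured again after rTMS, is reported as a separate outcome and not used to set the test pulse.

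This concerns the measurement pulse only and leaves the rTMS intensity alone. The cost is one sentence in the procedure and one in the outcomes paragraph, with no added visit or test. If a fixed output was intended all along, the same sentences confirm it.

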# 2. Participant Information:

a. Description of participants in study:

Ten men and women with a diagnosis of left hemisphere stroke and age >18 years will be recruited to participate in this pilot project.

- b. Approximate number of participants: 10
- c. Vulnerable populations as participants (check all that apply):

Prisoners[	
Pregnant women	
Fetuses / neonates	
Minors	

NOTE: Researchers must comply with the federal mandate to report child abuse. See instructions for details.

d. Age (or age range) of participants: > 18 years

Provide the rationale for inclusion/exclusion on the basis of age:

- 1. This study will not include individuals age below 18 years for a few reasons. Stroke is relatively uncommon in persons younger than 18 years. Further, rTMS safety data in children and adolescents are less well-established. We exclude individuals younger than 18 years for both scientific merit and safety concern.
- e. Sex of participants ...... Both

Provide the rationale for inclusion/exclusion on the basis of sex:

If yes, provide a description of the exclusion criteria and the rationale for using these criteria:

g. List and provide rationale for any other inclusion/exclusion criteria:

Inclusion criteria:

- Age above 18 years
  Stroke is very unlikely in individuals age below 18 years. Further, there are limited data to support the safety of rTMS in individuals younger than 18 years.
  - Diagnosis of Left hemispheric stroke at least 6 months ago
    Left dorsolateral prefrontal cortex has been shown to play an important role in human dual-task performance. We therefore specifically target those with left hemispheric lesion since they demonstrate greater deficits in dual-tasking. We exclude acute and subacute (< 6 months) stroke because spontaneous recovery is very likely to occur

during acute and subacute phases. This will lead to difficulty in result interpretation with the current single group design.

- First time stroke OR complete gait recovery from prior stroke
  Individuals with more than one stroke often have more than one lesion location or involve more than one hemisphere. This would potentially complicate the rTMS application. We therefore exclude those with multiple strokes such that our sample can be more homogenous.
- 4. Able to walk independently for at least 10 meters with or without walking aids 2.Participants are required to walk independently for the behavioral testing.

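### With 10 participants, site order can be balanced only approximately over three visits, and the ANOVA has no visit term, so any practice across visits would stay in the error and reduce power

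*Combined protocol and SAP*

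**What the plan says.** Section 2 (Participant Information) gives "Approximate number of participants: 10" and, in the rationale for excluding recent stroke, refers to "the current single group design".

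Section 4 (Research Procedures), item 3, says "Each participant will be tested for 3 visits", with one target per visit: "hot spot of the right tibialis anterior at the M1, left SMA, or left DLPFC". On sequence it says only "The order will be pseudo-randomized and counterbalanced within each group". It gives no list of orders, no number per order and no method of assignment.

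Section 4, item 4, gives the primary analysis: "The dual-task cost will be compared across three rTMS protocols using repeated measure ANOVA". For the GaitRite measures and MEPs it adds "These measures will be analyzed using repeated measure ANOVA as well". No term for visit, order or period is mentioned. Every visit opens with a full assessment before rTMS and repeats the tests afterwards, but the plan does not say whether the pre-rTMS value enters the ANOVA.

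**The concern.** The research question is a within-person comparison of three sites, each tested on a different day. No sham condition or separate control group is described, so the ordering of sites is the only stated protection against change over time. The protocol takes that threat seriously elsewhere: it excludes recent stroke because spontaneous recovery would be hard to separate from treatment in one group.

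Practice is a plausible change of the same kind. Each assessment has three dual-task walks and three seated counting bouts, and it is done before and after rTMS. That makes 12 bouts of serial subtraction per visit, 24 before visit 3 begins and 36 in all.

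Two consequences need separating. If sites are not spread evenly over visits, part of a practice effect is credited to the site that falls later. Even when they are spread evenly, a model without a visit term leaves the visit-to-visit shift in its residual, which can hide a real difference between sites.

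**Working it through.** The plan contains no power, SD or effect-size figure to reproduce. The check takes N = 10, three sites and three visits from the protocol. It assumes a within-person SD of 10 cost points, linear practice of p = 2.5, 5 or 10 points per visit (0.25, 0.5 or 1.0 SD), two-sided alpha 0.05, and one post-rTMS dual-task cost per visit as the analysed value.

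**1. Can the order be balanced?** Three sites have 3! = 6 orders, and a Latin square uses 3 of them. 10 = 3×3 + 1 = 6 + 4, so equal site-by-visit counts are impossible. The closest counts are 4/3/3, 3/4/3 and 3/3/4.

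**2. How much bias does that leave?** Mean visit number by site:

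- (4×1 + 3×2 + 3×3)/10 = 1.9
- (3×1 + 4×2 + 3×3)/10 = 2.0
- (3×1 + 3×2 + 4×3)/10 = 2.1

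The largest gap is 0.2 visit, so the bias in a site contrast is at most 0.2p: 0.5, 1.0 or 2.0 points. The contrast's standard error with an undisturbed error term is √(2×100/10) = 4.47 points.

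**3. What happens to the error term?** There are 30 observations. Participant plus site leaves 30 − 1 − 9 − 2 = 18 error df; adding visit leaves 16. Linear practice contributes a visit sum of squares of 10×(1 + 0 + 1)×p² = 20p². Of this, 10×(0.01 + 0 + 0.01)×p² = 0.2p² falls into the site sum of squares. The remaining 19.8p² stays in the residual. The expected error mean square is therefore 100 + (19.8/18)p² = 100 + 1.1p².

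| p per visit | Error MS, no visit term | √(MS/100) |
|---|---|---|
| 2.5 | 106.9 | 1.034 |
| 5 | 127.5 | 1.129 |
| 10 | 210 | 1.449 |

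With a visit term the error mean square returns to 100. Because site and visit are not quite orthogonal, the contrast variance rises by 10/9.9, about 1%, or 0.5% on the standard error. Dividing the last column by 1.005 gives 1.029, 1.124 and 1.442. To within a percentage point, omitting the visit term makes the standard error about 3%, 13% and 44% larger.

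**4. What does that do to the test?** Simulation of the 4/3/3 layout, 20,000 runs, with one site assumed to differ by 1.0 SD:

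| Practice per visit (SD) | Type I error, no visit term | Power, no visit term | Power, visit term |
|---|---|---|---|
| 0 | 0.050 | 0.55 | 0.54 |
| 0.25 | 0.046 | 0.53 | 0.55 |
| 0.5 | 0.028 | 0.43 | 0.54 |
| 1.0 | 0.005 | 0.18 | 0.54 |

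With the visit term, type I error stays between 0.051 and 0.054.

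**5. Would exact balance be enough?** No. At N = 12, with four participants in every site-by-visit cell and practice of 0.5 SD per visit, the error mean square is still 1.27 times its true value. Power is 0.53 without a visit term and 0.65 with one.

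**The case against.** The strongest reply is that every visit carries its own pre-rTMS assessment. If the ANOVA used change within the visit, or a site-by-time interaction, a stable shift between visits would cancel from both the contrast and its error. Only learning that differs within visits, for instance steeper at visit 1, would remain. This stands as a condition on the point. It does not remove it, because the plan describes the comparison as dual-task cost across protocols and gives the pre-rTMS value no role.

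It can also be said that the SD and practice rates come from outside the documents, that a new random starting number on each trial limits memorised sequences, and that at 0.25 SD per visit the loss is negligible (power 0.53 against 0.55). All of this is fair. The figures show a range and do not predict what will happen.

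A reader might infer more: that the failure to balance exactly biases the site comparison in a way that matters. The documents do not support that. The protocol says the order is counterbalanced, which rules out a free random draw. An unconstrained draw would give an average gap of about 0.54 visit, but that is not the stated design. Near-balance is normal in a small crossover, and since N is only approximate, 9 or 12 would balance sites over visits exactly. Nor does the reference to each group point to a second group; Section 2 describes one, and the phrase has no analytic effect.

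**Conclusion.** The point holds in a limited form. Counterbalancing of 10 participants over three sites and three visits can only be approximate, and under the best layout the resulting bias is at most 0.2 of one visit's practice effect. The omission that matters is the visit term. Without it, a practice effect enlarges the standard error of a site contrast by about 3%, 13% or 44% at 0.25, 0.5 or 1.0 within-person SD per visit.

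Under near-balance the test becomes conservative, so a reader should not infer a risk of false positives; the loss is in power. The size rests on an assumed SD, an assumed linear practice effect, and the analysis using one post-rTMS value per visit. If there is no practice, or if same-visit change is analysed and practice is stable within visits, little or nothing is lost. The change is worth making because it costs very little when practice is absent and protects the main comparison when it is present.

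**What to change.** **Analysis (Section 4, item 4).** Analyse dual-task cost and the secondary outcomes with a linear model containing participant, site and visit (1, 2, 3). Each participant fills only three of the nine site-by-visit cells, so visit cannot be added as a second fully crossed factor in a conventional repeated measures ANOVA. A Latin-square-type or mixed model is needed. State in advance whether the pre-rTMS value already collected at each visit enters as a covariate or through change from it.

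**Order (Section 4, item 3).** Replace the sentence with: participants are randomly assigned to a prepared list of all six orders once plus four distinct repeats, chosen so that each site falls at each visit three or four times. This is met when the two orders left unrepeated never place the same site at the same visit; 6 of the 15 possible choices qualify. Describe the order as approximately balanced and delete the reference to groups. If the final number will not be 10, redraw the list before enrolment.

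**Cost.** A few sentences, 2 of 18 error df for visit and one more if the covariate is used. With no practice effect, the visit term takes power from 0.55 to 0.54 in the case simulated. No participants, visits or measurements are added. An unscored practice block at visit 1 is optional and not needed for this point.

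### The dual-task cost formula lacks inner parentheses: read literally it reduces to dual-task time minus 1, contrary to the sentence it sits in

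*Combined protocol and SAP*

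**What the plan says.** The definition is in section 4, Research Procedures, item 4 (Outcomes and data analysis). In words: "The primary outcome of this project is participant performance on the TUG test under single and dual-task conditions". The next sentence names the inputs: "The time taken to complete the TUG test under the two conditions will be used to derive dual-task cost". The formula follows in the same sentence as "TUG dual – TUG single /TUG single". The only parentheses enclose the whole expression; none groups the difference in the numerator. The analysis is then given: "The dual-task cost will be compared across three rTMS protocols using repeated measure ANOVA". The formula is not restated or corrected anywhere else in the document, and no worked value or analysis code is shown.

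**The concern.** Under the usual order of operations the division is done first, so the single-task time is divided by itself and disappears. What remains is the dual-task time less a constant, which is not a cost relative to single-task walking. It also subtracts a pure number from a time in seconds. The words of the sentence require both times, while the symbols use only one, so the two cannot both be followed.

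The slip matters because of where it sits: this is the sole formula for the primary analysis variable. An analyst who followed the symbols would run a different test from the one the words describe and report it under the name dual-task cost.

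**Working it through.** **Inputs.** The formula, the two named times and the ANOVA across three stimulation targets come from section 4, item 4. The sample size comes from section 2 ("Approximate number of participants: 10"). The documents give no TUG times, so every time below is an assumption in seconds, chosen only to show how the two expressions behave. The plan prints no value of the cost, so there is no figure to reproduce.

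**Algebra.** Write S for single-task and D for dual-task time, with S > 0.

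- As printed: D − S/S = D − 1.
- With inner parentheses: (D − S)/S = D/S − 1.

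The two differ in whether D is divided by S.

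**Same dual-task time, different single-task time.**

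- S = 10, D = 25: printed 25 − 1 = 24; bracketed 15/10 = 1.5.
- S = 25, D = 25: printed 25 − 1 = 24; bracketed 0/25 = 0.

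The printed form cannot tell these apart.

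**Same proportional cost, different walking speed.**

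| S | D | Printed, D − 1 | Bracketed, (D − S)/S |
|---|---|---|---|
| 10 | 12.5 | 11.5 | 0.25 |
| 20 | 25 | 24 | 0.25 |
| 30 | 37.5 | 36.5 | 0.25 |
| 40 | 50 | 49 | 0.25 |

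**Ordering within one person.** This is the comparison that a repeated-measures ANOVA uses.

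- Visit A: S = 20, D = 25: printed 24; bracketed 5/20 = 0.25.
- Visit B: S = 18, D = 24: printed 23; bracketed 6/18 = 0.33.

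The printed form makes visit A worse and the bracketed form makes visit B worse. The reversal needs single-task time to change between visits. If S were the same at both visits, D − 1 and D/S − 1 would order them the same way.

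**Effect on the ANOVA.** Subtracting 1 from every observation changes no sum of squares, so an ANOVA on the printed expression is exactly an ANOVA on D. One simulated data set of 10 people by 3 conditions illustrates this. Single-task times had mean 20 and between-person SD 5, with visit noise of SD 1. The ratio of dual to single time had mean 1.25 and SD 0.08, and there was no true difference between conditions. The results were F = 0.373 for the printed form, F = 0.373 for raw dual-task time and F = 0.662 for the bracketed form. One data set says nothing about typical size; it shows only that the printed and bracketed forms are different tests.

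**The case against.** The strongest reply is that the meaning is hardly in doubt. The variable is called a dual-task cost, both times are named as inputs, and a term that divides a quantity by itself would be pointless if meant literally. Nothing in the documents suggests that anyone has coded, or plans to code, the literal form. This stands, and it is why the point is minor.

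A reader might infer that the primary endpoint as a whole ignores single-task performance. The documents do not support that. The outcome is defined in words under both conditions, and the sentence holding the formula says that both times are used. Only the symbols drop the single-task time.

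A reader might also illustrate the harm by ranking two different people: 20 s and 26 s gives 25 printed and 0.30 bracketed, while 12 s and 20 s gives 19 and 0.67. The arithmetic is right, but the planned comparison is within person. A repeated-measures ANOVA already removes stable additive differences between people, even on raw dual-task times. What the printed form loses is the proportional scaling and any change in single-task time between conditions.

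Finally, the text was read from PDF by a program, and a stacked fraction could have been flattened. The slash appears inline, which makes this less likely, but it cannot be ruled out. Checking the source page would settle it. What survives is the conflict between the symbols and the sentence around them.

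**Conclusion.** The point holds as a notation error in the only formula for the primary analysis variable. The algebra is certain: as printed, the expression equals TUG_dual − 1 for any non-zero single-task time. The practical harm is conditional on someone following the symbols rather than the words. In that case the primary ANOVA would be a test of raw dual-task time and could order stimulation targets differently within a person whose single-task time changes between visits.

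The reversal and the F values rest on assumed or simulated times, so they show what can happen, not how often or by how much. The conclusion also assumes that the inline slash reflects the source. Severity is minor. The documents state no power calculation, and the planned number of participants does not depend on the formula, so no stated sample size or power figure changes.

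**What to change.** Print the endpoint as (TUG_dual − TUG_single)/TUG_single, and confirm that the analysis code uses that expression. The cost is one pair of brackets in the protocol and one check of the code; no procedure, visit or sample size changes. How the assessments before and after stimulation enter the model is a separate question that the missing brackets neither raise nor settle.
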